5.1. Numbers of Participants

Number to be screened: N £ 135Number to be enrolled: N = 50

Up to 135 individuals will be screened. Based on our prior experience with perimenopausal women and intervention studies involving transdermal E2, we estimate that 40% will fail the medical screening for TE2 eligibility, and an additional 20% will not be interested in participating.

It will be necessary to enroll 50 perimenopausal women because our prior experience also suggests that 30% (n=15) will not meet eligibility for TE2 upon further screening, yielding about 35 eligible for the randomized, cross-over study. We conservatively account for 15% (n =5) withdrawal following randomization, yielding 30 women who complete the protocol

Since this is a cross-over study design, all enrolled women will receive both the active TE2 condition and the placebo TE2 condition.

Recruitment: Participants will be recruited through the Menopause Clinics at the UNC Hospitals, and through the UNC Center for Women's Mood Disorders. Additionally, participants will be respondents to advertisements in local newspapers, social media, and mass email listservs seeking volunteers for research. To increase minority applicants, physicians who are African American or of other minority ethnic groups will be included as referral resources, and certain ads will particularly request minority volunteers.

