Rescue Procedures/Medications Not applicable. Adverse events resulting from transdermal E2 would warrant discontinuation of the medication as determined by the [name]. Discontinuation of estradiol does not require a tapering schedule and there would be no 'rescue' medication.

Adherence Monitoring/Evaluations Subjects will: 1) be educated on the importance of replacing patches every 7 days and we will develop an individualized behavioral strategy to enhance compliance; 2) record date of patch

application on their calendars and receive text/call reminders; **3)** bring used and unused patches to each visit; and **4)** be given extra replacement patches. Patch counts (both used and unused) will be conducted at each weekly visit as the 'real time' assessment of compliance. Retrospectively, we can evaluate compliance by comparing urinary E1G levels under each of the two treatment conditions (transdermal E2 and placebo). If compliant, mean E1G levels should be significantly higher under the active TE2 condition.

Concomitant Therapies All psychotropic and hormonal therapies are prohibited as would insulin use. Stable thyroid hormone supplementation is allowed as is stable blood pressure medication as long as the medication is effective at maintaining blood pressure below 160/100 mmHg. Medication use will be assessed by self-report during screening and again at enrollment via the Personal and Family Health History Questionnaire.

7. Schedule of Activities and Procedures

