7.8. Early Discontinuations

Data to be Collected

If a participant chooses to withdraw consent or discontinue with the study interventions no medical records data will be collected at any point, however the following procedures will employed:

- 1. We will ask participant the reason for their withdrawal and record that in in their file and in the study database
- We will attempt to meet with the participant for one last visit to collect used/unused patches to determine compliance up to that point, assess and document vitals, and collect any E1G stored or unused urine strips.
- 3. If the participant wishes to withdraw from the intervention conditions, we will ask if they remain willing to complete the self-report surveys, particularly the irritability symptom scale on a daily basis, throughout the remainder of time that would correspond to their 14 study visits as irritability symptomatology is the primary outcome variable.
- 4. If the participant withdraws during or after at least one of the Conditions (TE2 or Placebo), the study gynecologist, [name] will be unblinded and determine if the participant needs the progesterone intervention for uterine protection. If that is determined to be the case, in order to

maintain the blind for research staff and the PI, [name] will be the one to follow the participant and document menses onset, duration, and magnitude associated with the Prometrium.

Criteria for Intervention Discontinuation

An individual will be withdrawn from the study by the investigators under any of the following conditions:

- 1. Inability to tolerate the adhesive in the patches
- 2. If there is indication of psychological distress that impairs function and would warrant treatment. We will monitor the CES-D in real time, on a weekly basis. If the clinical cut point with diagnostic specificity for Major Depressive Disorder (score ≥ 16), [name] will follow-up to assess psychological distress and determine if the participant is able to continue in the study. [name] will determine the next course of action (i.e., participant may continue or will be withdrawn and referred to the UNC Center for Women's Mood Disorders)

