7.9. Enrollees May Drop Out

Participants may voluntarily withdraw from participation at any time, for any reason, with no penalty or loss of rights. The reasons for drop-out and missing data will be documented in/with the database. If a participant wishes to withdraw from the intervention conditions, we will ask if they remain willing to complete the self-report surveys, particularly the irritability symptom scale on a daily basis, throughout the remainder of time that would correspond to their 14 study visits as irritability symptoms is the primary outcome variable.

8. Statistical Analysis Plans

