8.1. Strategies that Apply to all the Aims

The statistical analysis plan was developed in collaboration with [name], biostatistician for the Department of Psychiatry. [name] will perform the analyses for this protocol under the supervision of [name]. Participant flow will be tracked and reported using the CONSORT flow diagram and recommendations for cross-over study designs. The following baseline predictors will be calculated to model outcome variables: baseline irritability (sum of 5-items on the III Temper scale of the IDAS), E1G variability (standard deviation of 14 every-other-day E1G collections), and neurophysiological (EEG) correlates of threat and frustration (e.g., theta and beta oscillatory activity, event-related potentials (ERPs)) during the Dot Probe and Affective Posner Paradigm EEG tasks. Statistical estimates of population parameters will be estimated and tabulated using the statistical models

described in statistical plan of specific aims, along with corresponding confidence intervals and standard errors to indicate precision. All hypothesis tests yielding large p-values will be reported as being inconclusive. All the p-values will be reported with 3 decimal places to indicate the accuracy. The outcome of the proposed study will be discussed within the study team and outcome-dependent exploratory analysis will be designed and performed to generate new hypothesis if it is deemed necessary by the team. We acknowledge that no p-value can reveal the plausibility, presence, truth, or importance of an association or effect. All the response outcomes will be visualized using either boxplots by treatment or scatterplots between predictors and outcomes.

We will conduct a sensitivity analysis with and without missing data by assessing the following: 1) point estimates from complete cases, and 2) mean imputed values based on the observed data.

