Aim 2a) The two repeated post-treatment EEG measures (theta, beta, ERPs) will be modeled as a function of fixed factors including baseline EEG measures (continuous), Condition status (TE2 or placebo; binary), and order of Condition (binary) in a linear mixed effects model with a random intercept accounting for the within-subject variance. The two-sided Wald test will test the significance of TE2 effects. 2b) Similarly, weekly irritability symptoms (3 weeks/Condition) will be modeled as a function of fixed factors including baseline irritability symptoms (continuous), Condition, and order of Condition in a linear mixed effects model with a random intercept accounting for within-subject variance. Although we hypothesize that E1G variability will predict outcomes in Aim 1 and Condition effects in Aim 2, we will examine E1G levels if analyses do not support variability. In the statistical models described above, all the estimates of treatment effect, along with 95% confidence interval will be reported in the tabulated forms. Whenever multiple testing is used in the analysis described, Benjamini-Hochberg Procedure will be used to adjust for multiple comparison. All the hypothesis tests that yield large p-values will be reported as being inconclusive. To evaluate the robustness of the proposed study, we will perform sensitivity analysis for all the important findings. More specifically, we will repeat all the statistical analysis by excluding some potential outliers that could be influential points. We expect the sensitivity analysis will preserve the direction of original point estimates from full samples. Based on the study design, there will be potential missing data points caused by subject drop-out, and we assume all the missingness will most like to be missing at random (MAR). Since the linear mixed effects model is capable of handling missing values, the analysis plan will not be affected because of missing data.

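### Section 8.1 uses single mean imputation without saying which mean, and no planned check examines outcome-driven loss tied to one condition

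*Combined protocol and SAP*

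**What the plan says.** Section 8.1, which applies to all aims, sets the missing-data sensitivity analysis as "1) point estimates from complete cases, and 2) mean imputed values based on the observed data". It does not say whether the mean is the woman's own, the condition's or the overall mean.

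Section 8.3 states that "we assume all the missingness will most like to be missing at random (MAR") and, because a mixed model can use incomplete records, that "the analysis plan will not be affected because of missing data". The only other sensitivity analysis there drops influential outliers. Multiple imputation, delta adjustment and tipping-point analysis appear nowhere in the document.

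On the amount and causes of loss:
- Section 5.1: "We conservatively account for 15% (n =5) withdrawal following randomization", leaving 30 of about 35.
- Section 5.3.2 gives time commitment as the main reason expected.
- Section 6 (rescue procedures): "Adverse events resulting from transdermal E2 would warrant discontinuation of the medication".
- Section 7.8: "An individual will be withdrawn from the study by the investigators under any of the following conditions". The list includes psychological distress that warrants treatment.
- Section 7.8, on women who choose to stop: "If the participant wishes to withdraw from the intervention conditions, we will ask if they remain willing to complete the self-report surveys".
- Section 7.9: "The reasons for drop-out and missing data will be documented in/with the database".

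Section 4 schedules one EEG session at the end of each condition.

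**The concern.** There are two separate problems.

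The first needs no doubt about MAR. Filling a gap with a mean and then analysing it as data adds values with no residual scatter. Depending on which mean is used, it also pulls the two conditions together. A check with these faults can disagree with a sound primary analysis, or look more precise than it is.

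The second concerns what the checks can reveal. If women who are doing badly leave during one condition only, the observed values in that condition are too good. The mixed model and the complete pairs then use a favourable selection, and mean imputation fills the gaps with values better than those lost. With no true effect, all of them move the same way. A reader could take their agreement as robustness, and the statement in 8.3 encourages that reading.

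**Working it through.** **1. The plan's own figure.** 35 x 0.15 = 5.25, about 5 women; 35 - 5 = 30. This reproduces section 5.1.

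**2. Set-up.** From the documents: 35 randomized, 5 lost (5.1); one EEG value per condition (4); a model with condition, baseline, order and a random intercept, tested by a two-sided Wald test (8.3). Assumed, because the documents give no values: total SD 1, within-woman correlation 0.5, order read as sequence, higher score worse. Set A (3,000 simulated trials per setting) removes 5 women together with their later values. Set B (2,000 per setting) removes the second period for 5 women.

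**3. Random loss.**
- Condition mean: reported SE 0.161 against a true 0.181-0.184 in set A (1 - 0.161/0.181 = 11%; 1 - 0.161/0.184 = 12.5%). In set B it is 0.167 against 0.179 (1 - 0.167/0.179 = 7%). False-positive rate 7.5% in set B and 7.4% and 8.8% in repeat runs, against 5.2-6.1% for the mixed model.
- Overall mean, true effect -0.50: -0.45 in set A, -0.457 in set B, about -0.47 in a repeat run. By hand for set B, 5 of 70 values are filled: 0.50 x (1 - 5/70) = 0.464.
- Own mean, true effect -0.50: -0.44 (set A).

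**4. Aim 1.** The predictor is the SD of 14 E1G values (8.1). Values filled with a woman's own mean add nothing to her sum of squares, but the divisor returns to 13. Her SD is therefore multiplied by sqrt((13 - k)/13) for k filled values: sqrt(11/13) = 0.92 for k = 2 and sqrt(9/13) = 0.83 for k = 4.

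**5. Outcome-driven loss in one condition (set A).** The chance of loss is assumed to rise by exp(1.5), about 4.5 times, per SD worse. Entries are mean estimates in SD.

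| Setting | Mixed model | Complete pairs | Overall mean | Condition mean |
|---|---|---|---|---|
| True 0, TE2 only, 25% of losses | -0.03 | -0.02 | -0.03 | -0.03 |
| True 0, TE2 only, 50% | -0.06 | -0.05 | -0.06 | -0.07 |
| True 0, TE2 only, 100% | -0.10 | -0.09 | -0.12 | -0.14 |
| True -0.50, placebo only, 100% | -0.39 | -0.40 | -0.32 | -0.36 |

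A repeat of the 50% row gave -0.053 for the mixed model. In the 100% null row, varying the loss ratio from 2.1 to 7.4 per SD and the correlation from 0.3 to 0.7 gives a mixed-model bias of 0.05-0.16 SD.

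**6. How far this depends on the mechanism.**
- Weaker dependence: if loss acts through distress correlated 0.3 with the EEG value, the ratio is roughly exp(0.3 x 1.5) = 1.6 per SD. The mixed-model bias is then -0.047 with all loss of this kind and -0.015 with half.
- Loss that follows severity in either condition alike: bias about 0 under the null. At a true -0.50 it is at most about 0.02 SD for the mixed model, complete pairs and condition mean.
- Loss in second-period placebo driven by a stable trait, true -0.50: mixed model -0.46, complete pairs -0.50, overall mean -0.37, condition mean -0.40.

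**7. What a delta analysis would show.** With all 5 losses in TE2, the estimate moves by 5/35 = 0.143 x delta: 0.07 SD at delta 0.5 and 0.14 SD at delta 1. With a 3/2 split it moves by 1/35 = 0.029 x delta. For an illustrative estimate of -0.50 with SE 0.176, the upper 95% limit is -0.50 + 1.96 x 0.176 = -0.155. Holding the SE fixed, it reaches zero at 0.155/0.143, about 1.1 SD. Neither planned check yields such a figure.

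**The case against.** Several points on the other side stand.

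- Complete pairs do address one departure from MAR. Under loss driven by a stable, unobserved trait they are unbiased where the mixed model is not. A reader might infer that the plan has no protection at all outside MAR; the design does not support that.
- The shared bias under a null effect needs loss that is both outcome-driven and specific to one condition. The documents make this possible but do not indicate it. Adverse events can tie loss to TE2, but nothing links them to theta or beta power. Distress withdrawals relate to mood but are not tied to a condition. Time commitment is the main reason expected.
- Irritability is better protected than EEG, because women who choose to stop are asked to continue rating. No irritability data were simulated here.
- Comparing how often a range of estimates contains the no-loss estimate proves little. With all loss outcome-driven in TE2, the range of the planned analyses does so in 8% of trials and a 0-1 SD delta range in 73%. But the delta range is about four times as wide (0.21 against 0.055 SD), and under purely random loss the planned range manages only 28%.
- The Wald test's false-positive rates of 6.7% and 7.3% (25% and 50% outcome-driven) are within simulation error of the 6.1% under random loss. Only 10.2%, at the upper bound, stands apart.
- Multiple imputation is itself a MAR method. Alone, it leaves the upper-bound bias at -0.10.

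None of this rescues mean imputation, whose faults appear under random loss.

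**Conclusion.** The point holds, as a minor to moderate weakness. Single mean imputation with an unspecified mean is a poor check under any mechanism: the SE is about 7-13% too small with a condition mean, and a true -0.50 shrinks to between -0.44 and -0.47 with an overall or own mean. The claim in 8.3 that missing data do not affect the plan holds only under MAR.

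The gap for outcome-driven loss in one condition is real but modest: about 0.05 SD or less if half the loss is of this kind, about 0.10 SD at an upper bound with strong dependence, and near nil under the null if loss does not differ by condition. The SE is near 0.18. These sizes rest on 5 of 35 lost and on the assumed correlation and loss ratios, and apply mainly to EEG. A reader might infer that the TE2 estimate will be materially biased. The documents do not support that; they show only that the planned checks could not say how far such loss would move it.

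**What to change.** Keep the mixed model as primary and complete pairs as a secondary check.

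1. **Section 8.1, Aim 2.** Replace mean imputation with multiple imputation by period, using sequence/condition, the baseline value and the other condition's value. Add weekly CES-D only after sections 4.3, 7.1 and 7.4 are reconciled on whether it is collected in Condition 1. Little is lost without it.
2. **Section 8.1, Aim 2.** Add one delta-adjusted tipping-point analysis of the imputed values over a prespecified range, for example 0 to 1 baseline SD worse, applied to TE2 only, placebo only and both. Read it against the recorded drop-out reasons. Define worse as higher theta, lower beta (the directions in section 3.2) and higher irritability. The plan gives no direction for event-related potentials, so run delta both ways.
3. **Aim 1.** Compute the E1G SD from observed samples, state a minimum number, and do not mean-impute E1G.
4. **Section 8.3.** Replace the sentence on missing data with a statement that the mixed model is valid under MAR given the modelled variables and that departures are examined in 8.1.

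The cost is SAP wording and modest extra analysis. In simulation, the multiple-imputation SE was 0.185 against 0.178 for the mixed model, in a sensitivity analysis only. The delta step does the work: in the 100% TE2-only null case the estimate moves from -0.10 to -0.03 and +0.04 at TE2 deltas of 0.5 and 1 SD. In the 100% placebo-only case (true -0.50) it moves from -0.39 to -0.46 and -0.53 at the same placebo deltas.

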8.2. Sample Description

A combination of graphical representation (e.g., boxplot), and tabulated summary statistics (e.g., sample size, sample mean, standard deviation, and range of values) will be used to describe baseline sample characteristics such as demographic, baseline measures, etc. for each treatment sequence. For outcome responses, both the graphical visualization and summary statistics will also be generated according to the treatments they received.

8.3. Aim-Specific Plans

Plans for Aim 1. The objective of Aim 1 is to define baseline relationships between E1G variability, irritability symptom severity and neurophysiological correlates of threat and frustration (e.g., theta, beta, and associated ERPs (continuous)). Linear regression models will predict irritability symptoms and EEG variables from E1G variability (3) and predict irritability symptoms from EEG measures (2).

Plans for Aim 2. The objective of Aim 2 is to determine whether TE2, versus placebo, will beneficially modify EEG variables and reduce irritability symptom severity. Normality assumption will be accessed using studentized residual and extreme outliers will be assessed individually.

Aim 2a) The two repeated post-treatment EEG measures (theta, beta, ERPs) will be modeled as a function of fixed factors including baseline EEG measures (continuous), Condition status (TE2 or placebo; binary), and order of Condition (binary) in a linear mixed effects model with a random intercept accounting for the within-subject variance. The two-sided Wald test will test the significance of TE2 effects. 2b) Similarly, weekly irritability symptoms (3 weeks/Condition) will be modeled as a function of fixed factors including baseline irritability symptoms (continuous), Condition, and order of Condition in a linear mixed effects model with a random intercept accounting for within-subject variance. Although we hypothesize that E1G variability will predict outcomes in Aim 1 and Condition effects in Aim 2, we will examine E1G levels if analyses do not support variability. In the statistical models described above, all the estimates of treatment effect, along with 95% confidence interval will be reported in the tabulated forms. Whenever multiple testing is used in the analysis described, Benjamini-Hochberg Procedure will be used to adjust for multiple comparison. All the hypothesis tests that yield large p-values will be reported as being inconclusive. To evaluate the robustness of the proposed study, we will perform sensitivity analysis for all the important findings. More specifically, we will repeat all the statistical analysis by excluding some potential outliers that could be influential points. We expect the sensitivity analysis will preserve the direction of original point estimates from full samples. Based on the study design, there will be potential missing data points caused by subject drop-out, and we assume all the missingness will most like to be missing at random (MAR). Since the linear mixed effects model is capable of handling missing values, the analysis plan will not be affected because of missing data.

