
Statistical Analysis Plans for Each Aim Study Duration	to the placebo TE2 condition. Irritability symptoms will be measured daily using the III temper subscale of the Inventory of Depression and Anxiety Symptoms. Theta and Beta oscillatory frequencies will be assessed at rest and in response to the Dot Probe task and the Affective Posner Paradigm administered at the last day of each condition. Urinary measures of E1G will be collected every day during the last week of each condition and measured using an enzyme immunoassay (Arbor Assays, Ann Arbor, MI), with sensitivity at < 22.5 pg/mL to generate to within subject variability in E1G (indexed by the standard deviation of E1G). Aim 1 Plans. Linear regression models will predict irritability symptoms and theta and beta frequencies in response to tasks from E1G variability (based on the standard deviation of seven daily E1G measurements) and predict irritability symptoms from theta and beta task-related frequencies. Aim 2 Plans. The two repeated post-treatment EEG measures (theta and beta task-related frequencies) will be modeled as a function of fixed factors including baseline EEG measures (continuous), Condition status (TE2 or placebo; binary), and order of Condition (binary) in a linear mixed effects model with a random intercept accounting for the within-subject variance. The two-sided Wald test will test the significance of TE2 effects. 2b) Similarly, daily irritability symptoms (3 weeks/Condition) will be modeled as a function of fixed factors including baseline irritability symptoms (continuous), Condition, and order of Condition in a linear mixed effects model with a random intercept accounting for within-subject variance.
Participation Duration	Sixteen weeks
Enrollment Duration	Two years

2. Introduction

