4.2. Experimental Design

We have selected a within subjects, double-blind, cross-over design because of the greater statistical power over a between subjects RCT and to minimize bias.

Participants are randomized (1:1), without stratification, to order of TE2 versus transdermal placebo. Participants will receive either three weeks of transdermal E2 (0.1 mg/day) or three weeks of transdermal placebo as their first condition (Condition 1) and the other treatment (active E2 or placebo) as their second condition.

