5.6. Randomization and Concealment

Using a within-subjects, cross-over, placebo-controlled, double-blind design, participants will be randomized (1:1) to either three weeks of transdermal E2 (0.1 mg/day) or to three weeks of transdermal placebo as their first condition (Condition 1) and will have the other treatment (active TE2 or placebo) as Condition 2. Randomization to order of conditions will not be stratified.

[name], statistical collaborator on the project and Director of the Psychiatry Biostatistics Core, will develop the randomization table and the UNC Hospitals Investigational Drug Services will manage the randomization.

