5.7. Blinding

The transdermal patches will be blinded by the UNC Hospitals Investigational Drug Services who will package active and placebo preparations into blinded, identical pouches. All study staff, investigators, and research participants will remain blind to subjects' order of active vs. placebo intervention conditions until final data collection is complete.

In the event of an adverse event that could be potentially related to the pharmacologic intervention, the gynecology collaborator, [name] will be unblinded to treatment to determine if the subject needs to be withdrawn. In that event, only [name] will be informed who will, with [name], determine the course of action for the participant (e.g., follow-up with their doctor, ultrasound if suspected DVT, etc.). [name] will not

be performing any assessments with research participants so her unblinding should not create bias in data collection, analyses, or interactions with other participants. Staff will not be informed as to the reason any particular subject is withdrawn.

6. Treatment Design: Procedures

Description

Using a within-subjects, cross-over, placebo-controlled, double-blind design, participants will be randomized (1:1) to either three weeks of transdermal E2 (0.1 mg/day) or to three weeks of transdermal placebo as their first condition (Condition 1). A three-week washout period will follow, and Condition 2 will follow the washout (placebo E2 if Condition 1 was active and active TE2 if Condition 1 was placebo). At the end of a subject's participation, each will be given Prometrium® (200 mg/day for 10 days).

Acquisition Investigational Drug Services will order the commercially available Climara® transdermal patches and the commercially available Prometrium® progesterone.

Storage Investigational drug services will store the Climara® and Prometrium® at a controlled room temperature of 77° stored away from heat, moisture, and direct light. Prometrium® will be dispensed in tight, light resistant containers. Climara® and the placebo patch will be dispensed in light resistant foil pouches. Participants will be instructed to store their study medications under the same temperature and light controlled conditions. Given the short duration of the intervention, there will not be a risk that the medications will expire.

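### The Aim 2 crossover models name no period effect if 'order of Condition' means the randomized sequence; define the term and list period

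*Combined protocol and SAP*

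**What the plan says.** Section 8.3 gives the Aim 2a fixed effects as baseline EEG, "Condition status (TE2 or placebo; binary), and order of Condition (binary) in a linear mixed effects model", with a random intercept. Aim 2b has the same structure: "baseline irritability symptoms (continuous), Condition, and order of Condition in a linear mixed effects model". The synopsis (section 1) repeats it: "order of Condition (binary) in a linear mixed effects model with a random intercept accounting for the within-subject variance". None of these places defines order, and none names a period, visit or time term.

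Elsewhere the word has a consistent use:

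- Section 4.2: women are "randomized (1:1), without stratification, to order of TE2 versus transdermal placebo".
- Section 5.6: "Randomization to order of conditions will not be stratified".
- Section 5.7: staff and participants stay blind to the "order of active vs. placebo intervention conditions until final data collection is complete".

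In each case order is the allocation, TE2 first or placebo first. Section 8.2 uses another name for that allocation when it promises summaries of "baseline measures, etc. for each treatment sequence".

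**The concern.** In a two-treatment, two-period crossover, each woman's TE2-placebo difference contains the treatment effect plus or minus any common change between the two periods. A period term removes that change; a sequence term cannot.

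A shift is plausible here. Condition 2 starts six weeks after Condition 1 starts (three weeks of treatment plus three of washout). The EEG tasks are given at visits 4, 7 and 13, so the two treated sessions are the second and third administrations. Women are selected for an ill temper score above 10 and a recent very stressful event (section 5.2.1), and both can ease with time. The three-week washout addresses carryover, which is a different matter.

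At stake are the precision of the TE2 estimate and, if completers are unequal by sequence, its bias. In addition, two analysts could code the same sentence as two different models.

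**Working it through.** **Link to the plan's own figure.** Section 9 claims 85% power for f = 0.25 with N = 30 and gives no within-woman correlation ρ. For two conditions, λ = N·m·f²/(1−ρ) on (1, 29) df, two-sided 5% (assumed; the plan states only 95% intervals).

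- ρ = 0.5: λ = 30·2·0.0625/0.5 = 7.5, power 75.4%.
- ρ = 0.61: λ = 3.75/0.39 = 9.6, power 85%.

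The plan's figure is therefore reachable under an assumed ρ. At ρ = 0.5, f = 0.25 equals a TE2 effect of √(7.5/30) = 0.5 SD of the paired difference, which is the effect used below.

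**What cancels.** Let τ be the TE2 effect, π the shift from Condition 1 to Condition 2, and D a woman's TE2-placebo difference. Sequence, baseline and random intercept drop out of D, leaving

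- TE2 first (n1 women): D = τ − π + error
- placebo first (n2 women): D = τ + π + error

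Fitted mixed models on simulated complete data confirm this. At 18/12, adding sequence left the TE2 estimate and SE at 0.5373 and 0.1867; adding period changed them to 0.4689 and 0.1828.

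**Formulas (SD of D = 1).**

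- Without period: bias = −π(n1−n2)/N, and the expected variance of D is 1 + π²·4n1n2/[N(N−1)].
- With period: the estimate is the half-sum of the two sequence means; bias 0, SE = ½√(1/n1 + 1/n2).

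For π = 0.5:

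- 15/15: variance 1 + 0.25·900/870 = 1.259, SE √(1.259/30) = 0.205, against 0.183 with period.
- 18/12: bias −0.5·6/30 = −0.10, SE √(1.248/30) = 0.204, against 0.186 with period.

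**Simulated power, τ = 0.5, N = 30, one value per condition (EEG).**

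| Shift | Completers | Bias, no period | Power, no period | Power, with period |
|---|---|---|---|---|
| 0 | 15/15 | 0 | 75% | 75% |
| 0 | 18/12 | 0 | 75% | 74% |
| 0 | 20/10 | 0 | 75% | 70% |
| 0.25 | 15/15 | 0 | 73% | 75% |
| 0.25 | 18/12 | 0.05 | 64% if opposing TE2, 81% if favouring | 74% |
| 0.5 | 15/15 | 0 | 67% | 75% |
| 0.5 | 18/12 | 0.10 | 47% if opposing TE2, 84% if favouring | 74% |

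Without period and with shift 0.5, type I error is about 3% at 15/15 and about 10% at 20/10; with period it is 5%.

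**Correlation range.** With outcome SD 1, 15/15 and shift 0.5, power without and with period runs from 54% and 61% at ρ = 0.3 to 86% and 93% at ρ = 0.7.

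**Repeated irritability ratings (Aim 2b).** Section 8.3 has three weekly ratings per condition; the synopsis has daily ratings, so 21. With independent residuals (assumption), SD of the condition-mean difference 1 and shift 0.5, power at 15/15 falls by only about 0 to 2 points without period. At 18/12 the bias is still 0.10; if it opposes TE2, power is about 57% to 59% without period and 75% to 77% with it. Random-intercept fits with 12 TE2-first and 18 placebo-first gave mean estimates of 0.601 without period and 0.503 with it, for a true value of 0.5 (three ratings).

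**Chance of imbalance.** Section 5.1 expects 35 randomized and 5 withdrawals. Under unrestricted allocation, P(18/12 or worse among 30) = 36%, or 18% in each direction. If 18 and 17 are allocated and withdrawals are random, an 18/12 split requires all five to come from the group of 17: C(17,5)/C(35,5) = 6188/324632 = 1.9%.

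**The case against.** The strongest counter-argument is the wording. The protocol uses Condition 1 and Condition 2 as names for first and second position, so order of Condition could mean position, and section 8.2 has a separate term for sequence. If the authors meant position, period is already in the model. The list of terms is also open-ended, and section 4.3 mentions covariates that section 8.3 omits. This leaves real doubt about intent. It does not rescue the text: all three uses of order in the design sections mean sequence, and an open list does not supply a structural term.

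The size can also be challenged, and these limits stand:

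- No shift is quantified in the documents, and the pre-randomization EEG session and four-week baseline may absorb some early practice effect and regression to the mean.
- With balanced completers there is no bias, and the irritability analysis loses almost nothing.
- Section 5.6 does not rule out blocking, so a marked imbalance may be rare.
- Averaged over unrestricted allocation, type I error is 5% with or without period. Power averages 66% against 74% for shift 0.5, but 73% against 74% for shift 0.25.
- At d = 1.11, power without period is still 99.9% with an opposing shift of 0.5 at 18/12.

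**Conclusion.** The point holds. On the best-supported reading, neither Aim 2 model adjusts for period, and the listed sequence and baseline terms cannot do that job. For a medium TE2 effect and a shift of 0.5 SD of the paired difference, the EEG analysis loses about 8 points of power with balanced completers. At 18/12, both aims carry a bias of 0.10, a fifth of the assumed effect, in either direction. With a shift of 0.25 the consequences are about half that bias and 2 points of power at balance. These are scenarios: shift, correlation and allocation method are assumptions, and the chance of an 18/12 or worse split runs from about 2% to 36% across the two allocation schemes considered. The plan's large-effect power claim is not threatened; the medium-effect claim and the reported estimates and intervals are. On the other reading only a definition is missing. The change should be made because it is cheap and removes an analyst's choice.

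**What to change.** In sections 1 and 8.3, define order of Condition as the randomized sequence (TE2 first or placebo first) and add period (Condition 1 or Condition 2) as a fixed effect in both the Aim 2a and Aim 2b models. If order was meant as first or second position, state that it is the period term. Keep the pre-study baseline. Use the washout irritability ratings only descriptively to look for carryover, which a period term does not remove.

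The cost is wording and one degree of freedom, with no new data. If no shift exists, the term costs nothing at 15/15, about 2 points of power at 18/12 and about 5 at 20/10. The change should be made before unblinding.
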